To investigate feasibility of an 8-week progressive home-based exercise intervention and change in patient-reported symptoms and pelvic tilt, in a prospective cohort of patients with radiographic verified acetabular retroversion, and excessive anterior pelvic tilt.

Primary hypothesis:

In a paired design, the improvement in '*The Copenhagen Hip and Groin Outcome Score*' pain-subscale (HAGOS questionnaire), following an 8-week exercise intervention, will be larger in comparison with the prior control period.

Secondary hypotheses:

- The exercise intervention is feasible in terms of adherence to exercise, exercise-related pain, drop-outs, and adverse events.
- The improvements in the remaining HAGOS subscale scores on symptoms, level of function, and quality of life, following an 8-week exercise intervention, will be larger in comparison with the control period.
- The improvements in the EQ-5D-3L questionnaire, following an 8-week exercise intervention, will be larger in comparison with the control period.
- The reduction in the degree of anterior pelvic tilt evaluated by EOS imaging, following an 8-week exercise intervention, will be larger in comparison with a control period.

STUDY METHODS

Design

The study was designed as a single-center, non-consecutive, unblinded prospective cohort study using patients as their own controls. The change between an 8-week control period prior to the intervention and the following 8-week exercise period will be reported.

Exercise intervention

A physiotherapist (the project manager) informed the patients about the relation between the hip condition and the purpose of the exercise program, provided advice on activity and sports modification, and instructed in exercises. The exercise program was an 8-week progressive home-based exercise intervention with optional, supervised booster-sessions and opportunity to contact the project manager by mail or phone in case of questions regarding the exercise program. After the 8-week exercise period was completed, the patients were encouraged to continue with the exercise program for another 16 weeks.

The exercise program was standardized and non-supervised consisting of four general elements: stretching for posterior pelvic tilt mobility, strengthening hip abductors and extensors, improving body core stability, and movement control for actively tilting and/or keeping the pelvis posteriorly.

Statistical Analysis plan

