#5 Strengthening the hip external rotators (Clamshell)	2 sets of 10 reps.	3 sets of 10 reps.	4 sets of 10 reps.
#6 Spinal mobility (Cat & Camel)	1 set of 10 reps.	1 set of 10 reps.	1 set of 10 reps.
#7 Movement control in lying (Dying bug)	2 sets of 10 reps.	3 sets of 10 reps.	4 sets of 10 reps.
#8 Movement control in lying (Single leg pelvic tilt)	2 sets of 10 reps.	3 sets of 10 reps.	4 sets of 10 reps.
#9 Strengthening the hip extensors	2 sets of 10 reps.	3 sets of 10 reps.	4 sets of 10 reps.
#10 Core stability (Dynamic plank)	2 sets of 10 reps.	3 sets of 10 reps.	4 sets of 10 reps.
#11 Movement control in standing (Sup. pelvic tilt)	1 set of 10 reps.	1 set of 10 reps.	1 set of 10 reps.
#12 Movement control in standing (Unsup. pelvic tilt)	1 set of 10 reps.	1 set of 10 reps.	1 set of 10 reps.

Abbreviations: Sec.=Seconds, Reps. Repetitions, Sup.=Supported, Unsup.=Unsupported

Selection of subsample for physical performance assessment

A subsample (20 patients) of the included patients was randomly selected to be investigated for isometric muscle strength, kinematic and kinetic outcomes during gait and functional tasks in a 3-dimensional motion laboratory. The explorative outcomes will be reported in secondary analyses not specified in the current SAP.

Sample size

The sample size calculation was based upon paired means calculation. The minimal clinical important difference (MCID) for the HAGOS pain-subscale was estimated being 10 % (half a standard deviation) (30). A minimum of 36 patients was required (10 % pre-posttest difference on HAGOS pain-subscale, SD=20.6 (30), alpha = 0.05, power = 80 %). An additional of four patients were added due to the risk of dropout.

Stopping guidance

There was no overall stopping guidance in the study or interim analysis of adverse effects. However, the training was stopped, and the referring physician contacted if individual patients experienced pain above 4 on a 0-10 Numeric Ranking Scale related to the training program, that could not be reduced by adjusting the exercises during a booster-session.

Timing of analysis

The primary endpoint was after the 8-week exercise period.

There were four time points at which the outcomes were measured, framing three consecutive periods: control period, exercise period, and an additional 16-weeks exercise period. Analysis of data from the 16 weeks of additional exercise is not a part of this SAP.

Timing of outcome assessments

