Time points at which the outcomes were measured are presented in Table 1. Outcomes are defined in the *Analysis* section.

Table 1 – Timing of outcome assessments

Outcomes	Control period	Baseline	Primary endpoint
		Minus 8-weeks before exercise intervention	Start-up of exercise intervention
Primary outcome			
PROM: HAGOS pain subscale	x	x	x
Secondary outcomes			
PROM: HAGOS remaining five subscales	x	x	x
EQ-5D-3L	x	x	x
EOS scanning: Pelvic tilt	x	x	x
Explorative outcomes			
PROM: Global Perceived Effect			x
Oxford Hip Score	x	x	x

Abbreviation: PROM (Patient-Reported Outcome Measure)

STATISTICAL PRINCIPLES

Descriptive data and fitted regression residuals from the mixed-effects linear regression model will be visually assessed for Gaussian distribution by use of QQ-plots and frequency histograms, and statistically tested using the Shapiro-Wilk test. Parametric and/or non-parametric statistical analyses will be used appropriately. A two-tailed P-value of $P \leq 0.05$ will be considered statistically significant, and estimates will be presented with 95% confidence intervals. A primary analysis following the Intention-To-Treat (ITT) principle and a secondary Per Protocol (PP) sensitivity analysis will be conducted (elaborated later in the *Analysis* section).

Adherence

Adherence to the exercise program (frequency) was recorded in a self-reported training diary. Adherence was defined as at least 75% completion of the prescribed exercise program in the 8-week period. The patients were instructed to exercise 3-4 times a week (i.e. 24-32 times over eight weeks) accordingly. Thus, at least 18 exercise sessions (75% of 24 exercise sessions), must have been completed to achieve acceptable compliance.

Exercise-related pain and adverse events

Exercise-related pain was recorded in a self-reported training diary, from 0-10 on a Numeric Ranking Scale (NRS) before, during and after exercising. A level of hip-related pain equal to and above 5 was defined as alarming values and subsequently adjustments were done as described above. Potential adverse events were noted in the training diary or reported by phone and email to the project manager. The use of hip-related analgesics and general comments on the exercise program were noted in the diary.

Protocol deviations

The following minor adjustments/additions were made after trial registration on Clinicaltrials.gov and inclusion of the first patient.

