- The assessment of feasibility was added to the study objective because of the novelty and potential importance of the exercise program.
- The secondary outcome '*Radiographic measurement of pelvic tilt in the frontal plane, defined as the distance (in mm.) between the sacro-coccygeal joint and the symphysis*' was changed to the '*Radiographic measurement of pelvic tilt in the sagittal plane, defined as the angle (in degrees) between a horizontal line and a line connecting the upper border of the symphysis with the sacral promontory*'. From inspecting our radiographic data, we learned that pelvic tilt measured in the sagittal plane were more reliable compared to frontal plane images. Moreover, the adjustment resulted in that no images had to be excluded due to poor image quality.
- Due to two dropouts early in the study, two additional patients were recruited. However, since only one patient subsequently dropped out, a total of 39 patients completed the training out of 42 included patients.
- Three patients did not get the last EOS-scanning done after the end of the exercise period due to pregnancy (n=2) and a defect apparatus (n=1).

TRIAL POPULATION

Patients between 18 to 40 years old were included from Odense University Hospital outpatient clinic (Denmark), with verified acetabular retroversion (positive COS and PWS) from a frontal pelvic radiograph in standard standing position, not eligible for periacetabular osteotomy and able to take part in the intervention. Patients were excluded if they had a pelvic-tilt-ratio greater than 0.5 (31) (the height of the obturator foramen divided by the height of the lesser pelvis) indicating posterior pelvic tilt, radiographic sign of hip osteoarthritis (< 2 mm. joint space), previous lumbar, pelvic or hip related surgery, conditions not allowing exercise therapy, a body mass index (BMI) above 35 and not understanding spoken and/or written Danish language.

Flowchart of patients' progress through the study is presented in Figure 1.

Statistical Analysis plan

[figure not shown]

Figure 1 – Flowchart of patients' progress through the study

Patient characteristics are presented in Table 2.

Table 2 – Patient characteristics at the beginning of the control period (n=42)

Patient characteristics	
Sex, male/female, n (%)	
Age, years	
BMI, kg/m ²	
Height, m	
Weight, kg	
Affected hip	
Bilateral, n (%)	
Left, n (%)	
Right, n (%)	
Patient-reported outcome measures	
HAGOS, score from 0 to 100	
Pain	
Symptoms	

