Change between-period comparisons in the remaining five HAGOS subscales, EQ-5D-3L, and pelvic tilt will be tested using a mixed-effects linear regression model as described in the primary analysis.

Post hoc analysis:

A responder/non-responder analyses will be carried out by investigating the exercise period change on the HAGOS pain subscale (Y-axis) against HAGOS pain subscale baseline score, pelvic tilt, age and BMI (X-axis), respectively. The *Minimal Clinical Important Difference* (MCID) of 10 % in the HAGOS pain subscale (30) will be marked as a horizontal lines ($Y=\pm 10$). Patients with change scores equal to and larger than the MCID will be defined as responders to the exercise intervention.

Statistical Analysis plan

Table 3 – Outcome change scores

	Control period change Mean, [95% CI], P-value	Exercise period change Mean, [95% CI], P-value	Between periods change Mean, [95% CI], P-value
Primary outcome			
HAGOS pain			
ITT			
PP			
Secondary outcomes			
HAGOS symptoms			
ITT			
PP			
HAGOS ADL			
ITT			
PP			
HAGOS Sp/Re			
ITT			
PP			
HAGOS Ph/Ac			
ITT			
PP			
HAGOS QoL			
ITT			
PP			
EQ-5D-3-L			
ITT			
PP			
Pelvic tilt			
ITT			
PP			

Abbreviations: ITT=Intention To Treat (Mixed-effects linear regression model), PP=Per Protocol, ADL= *Physical function in daily living*, Sp/Re= *Physical function in Sport and Recreation*, Ph/Ac= *Participation in Physical Activities*, QoL= *hip and/or groin-related Quality of Life*

Clinical perspective

This study will provide information regarding feasibility and responder characteristics of a standardized progressive home-based training intervention for patients with symptomatic acetabular retroversion and excessive pelvic tilt.

REFERENCES

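### The post hoc responder plot sets exercise-period pain change against the start-up score that is subtracted to form it, so patients with worse starting pain will tend to look like responders even if response does not differ

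*SAP*

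**What the plan says.** Under Analysis, Post hoc analysis, the SAP plans a responder analysis by "investigating the exercise period change on the HAGOS pain subscale (Y-axis) against HAGOS pain subscale baseline score", and likewise against pelvic tilt, age and BMI. Horizontal lines are drawn at +10 and -10 points, and "Patients with change scores equal to and larger than the MCID will be defined as responders to the exercise intervention". No model, test or caution accompanies the plot.

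The paragraph does not say which visit supplies the baseline score. Table 1 (Timing of outcome assessments) has columns for the control period, baseline and primary endpoint. Its sub-headings give minus 8 weeks and then "Start-up of exercise intervention". The table is shifted in the extracted text, but the order of the labels makes start-up the natural baseline. Table 2 describes a different visit: "Patient characteristics at the beginning of the control period (n=42". It does not call that visit baseline.

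The Clinical perspective section states the use: "This study will provide information regarding feasibility and responder characteristics". The responder plot is the only analysis in the SAP that addresses the second of these.

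**The concern.** Write Y1, Y2 and Y3 for HAGOS pain at minus 8 weeks, at start-up and at the primary endpoint. If baseline means start-up, the panel plots Y3 - Y2 against Y2. A patient who happens to score low at start-up, through measurement error or a bad week, sits to the left on the X-axis and gains on the Y-axis simply by returning to the usual level. A negative slope follows even if exercise does nothing, or does the same for everyone.

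HAGOS runs from 0 (extreme problems) to 100 (none), so the panel would tend to present worse starting pain as a characteristic of responders. The plot contains no unexercised reference from which a reader could judge how much of the slope is artefact. Pelvic tilt, age and BMI are not components of the change score and do not have this problem.

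**Working it through.** **Inputs from the SAP**
- Responder threshold: a gain of 10 points (Post hoc analysis).
- SD 20.6 and a difference of 10 (Sample size). The threshold is described as "estimated being 10 % (half a standard deviation", which supports reading 20.6 as a between-patient SD.
- 39 of 42 patients completed the training (Protocol deviations).

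**Assumptions**
- The between-visit correlation rho is not in the SAP. It is taken as 0.5, 0.7, 0.8 and 0.9.
- Scores are normal with equal variance at each visit.
- The median split below is for illustration; the SAP does not plan one.

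**The plan's own figure.** The normal approximation for paired means gives (20.6 × (1.960 + 0.842)/10)² = 33.3, so 34. The exact paired t-test has power 79.7% at n = 35 and 80.8% at n = 36, so the stated 36 reproduces. That calculation uses 20.6 as the SD of the paired difference. If 20.6 is also the between-patient SD, then 20.6 = 20.6 × √(2(1 - rho)), so rho = 0.5, the worst end of the range.

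**Expected pattern with no differential response**
- Slope of Y3 - Y2 on Y2: -(1 - rho).
- Correlation of Y3 - Y2 with Y2: -√((1 - rho)/2).
- Variance in change explained by baseline: (1 - rho)/2.
- Given a start-up score z SDs from the mean and no exercise effect, P(gain ≥ 10) = P(Z ≥ [10 + (1 - rho) × 20.6 × z] / [20.6 × √(1 - rho²)]), with Z standard normal. This is integrated over each half of the distribution of z.

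| rho | 0.5 | 0.7 | 0.8 | 0.9 |
|---|---|---|---|---|
| Slope | -0.50 | -0.30 | -0.20 | -0.10 |
| Correlation | -0.50 | -0.39 | -0.32 | -0.22 |
| Variance explained | 25% | 15% | 10% | 5% |
| Responders below the median start-up score | 46% | 37% | 30% | 18% |
| Responders above the median | 17% | 16% | 15% | 10% |
| Share of responders below the median | 73% | 69% | 67% | 64% |

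**With a uniform 10-point gain for every patient.** The responder rates below and above the median become 67% and 33%, 63% and 37%, 60% and 40%, and 57% and 43%. The share of responders below the median is 67%, 63%, 60% and 57%. The artefact therefore does not depend on exercise being ineffective.

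**Visibility at n = 39.** The SAP plans no test. If the correlation were tested, the artefact alone would give two-sided P < 0.05 in about 91% (rho 0.5), 69% (0.7) or 28% (0.9) of studies.

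**If the minus-8-week score is plotted instead.** The expected slope of Y3 - Y2 on Y1 is zero when all pairs of visits are equally correlated. If correlation decays with time as AR(1), it is rho² - rho = -rho(1 - rho): -0.25, -0.21, -0.16 and -0.09.

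**Contrast with the control period.** Under equal correlation and no effect, the slope in the exercise period minus the slope in the control period (Y2 - Y1 on Y1) averages 0 over simulated studies of 39 patients. Its SD is about 0.19, 0.17, 0.15 and 0.12. If patients entered only with below-average first scores (an assumption), the mean difference is about -0.09, -0.14, -0.14 and -0.11, so the contrast does not cancel the artefact fully.

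**The case against.** Five points can be made for the plan.

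1. **The visit is not fixed.** Table 2 lists all four X variables at the start of the control period, and plotting that score would remove the direct coupling. This stands in part. However, Table 1 attaches the label baseline to start-up, and the minus-8-week score is free of the problem only under equal between-visit correlation.
2. **The analysis is minor.** It is headed post hoc, is graphical and untested, and supports no stated hypothesis. This is true and limits the weight of the point. The SAP nevertheless fixes the axes, the cut-off and a causal label for responders, and names responder characteristics as an output.
3. **The size depends on an assumed rho.** At 0.9 the baseline explains only 5% of the variance in change, and the shares of responders are smaller if there is a real uniform gain. That stands. The direction is the same throughout the range, and the gap in responder rates is wider, not narrower, under a uniform gain.
4. **The lines at ±10 give some warning.** With no effect, as many patients would fall below -10 as rise above +10. That helps in judging the overall effect, but it does not remove the slope against baseline.
5. **The remedy is imprecise and may not cancel everything.** This also stands, so the contrast should be presented as a guard against over-reading and not as a powered test.

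**Conclusion.** The concern holds. On the natural reading of Table 1, this one panel of four will tend to show a negative slope and an excess of low-baseline responders without any differential response. For rho from 0.5 to 0.9, the spurious correlation runs from -0.50 to -0.22. With no exercise effect, the share of responders below the median runs from 73% to 64%.

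The size rests on the assumed rho, an SD of 20.6 and equal variances. The direction would reverse only if scores spread out markedly after exercise, that is, if rho times the end-of-exercise SD exceeded the start-up SD. The primary between-period analysis and Table 3 are not affected. This is a change that should be made, though it does not bear on the main conclusion of the study.

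**What to change.** In the Post hoc analysis section:
- State which visit supplies the baseline score on the X-axis.
- Place the control-period plot (Y2 - Y1 against Y1, same ±10 lines) beside the exercise-period plot as the no-exercise reference.
- Base any statement about baseline pain and response on the difference between the two slopes, with a confidence interval that respects the pairing, for example from a patient-level bootstrap.
- State that the raw change-against-baseline pattern is not evidence of differential response.
- State that the contrast is imprecise at n = 39 and assumes stable variance and correlation across visits, which fails if patients entered at a symptomatic low.
- Treat a plot against the minus-8-week score as supplementary at most.

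The cost is one extra panel, one interval and a few sentences, all from the three scores already collected. The downside is imprecision: the SD of the slope difference, about 0.12 to 0.19, is of the same order as much of the artefact itself (0.10 to 0.50). The contrast therefore protects against over-interpretation more than it detects true effect modification.

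### The post hoc responder rule credits any exercise-period gain of 10 points or more to exercise and plans no matching count for the 8-week control period

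*SAP*

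**What the plan says.** The Design section of the SAP describes an "unblinded prospective cohort study using patients as their own controls", with an 8-week control period followed by an 8-week exercise period. HAGOS pain is measured at all three time points that frame these periods (Table 1). The primary and secondary outcomes are all between-period changes.

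The Post hoc analysis paragraph departs from this. It rests on "investigating the exercise period change on the HAGOS pain subscale (Y-axis) against HAGOS pain subscale baseline score", and also against pelvic tilt, age and BMI. Lines are drawn at +10 and -10, and "Patients with change scores equal to and larger than the MCID will be defined as responders to the exercise intervention". No plot or count of control-period changes under the same rule is planned.

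The Clinical perspective section then makes the result a named output: "This study will provide information regarding feasibility and responder characteristics".

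**The concern.** The label is causal, but the quantity under it is an uncontrolled before-after change in one unblinded group. Some patients will gain 10 points over eight weeks without any treatment effect, and the control period is the plan's only means of showing how many. Table 3 reports the control-period change as a mean with a confidence interval and P-value, and a mean does not give the share of patients above a threshold. The line at -10 shows worsening, not background improvement.

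A second problem lies in the same figure. If the baseline score is the one taken at the start of exercise, as Table 1 appears to label it, that score is the X value and is also subtracted in the Y value. Error or temporary variation in it then produces a negative slope without any exercise effect.

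At stake is the reading of one named output: fluctuation could be reported as response, and a low starting score as a feature that predicts response.

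**Working it through.** **Inputs from the SAP.** Threshold 10 points on a 0-100 scale where higher is better (Post hoc analysis; Primary outcome definitions). Sample size: "10 % pre-posttest difference on HAGOS pain-subscale, SD=20.6", alpha 0.05, power 80%, minimum 36 patients. Two-sided testing (Statistical principles). 39 patients completed training (Protocol deviations).

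**Assumptions.** The SAP gives no within-patient correlation r between visits, so a range is used. Mean change is set to zero and changes are taken as approximately normal, although the scale is bounded. Visits are taken as equally variable and equally correlated.

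**Step 1: reproduce the sample size.** Paired t-test, noncentrality (10/20.6)·√n, n-1 degrees of freedom. Power is 0.797 at n = 35 and 0.808 at n = 36, so the minimum is 36, as stated. The calculation therefore uses 20.6 as the SD of change. However, the same section calls the MCID "estimated being 10 % (half a standard deviation", which would also fit a single-visit SD. Both readings are carried forward.

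**Step 2: share meeting the rule with zero mean change.** P(change ≥ 10) = 1 - Φ(10/SD of change).

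- 20.6 as SD of change: 1 - Φ(10/20.6) = 0.314, and 0.314 × 39 = 12.2 patients.
- 20.6 as single-visit SD: SD of change = 20.6·√(2(1-r)).

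| r | SD of change | Share ≥ 10 |
|---|---|---|
| 0.3 | 24.37 | 34.1% |
| 0.5 | 20.60 | 31.4% |
| 0.7 | 15.96 | 26.5% |
| 0.9 | 9.21 | 13.9% |
| 0.95 | 6.51 | 6.2% |

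**Step 3: regression to the mean**, if baseline is the start-of-exercise score and 20.6 is the single-visit SD. For a patient starting 1 SD below or above the mean, the expected change is +(1-r)·20.6 or -(1-r)·20.6, with conditional SD 20.6·√(1-r²).

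- r = 0.5: expected change ±10.3, SD 17.84. P(≥ 10) is 1 - Φ((10 - 10.3)/17.84) = 0.507 for the low starter and 1 - Φ((10 + 10.3)/17.84) = 0.128 for the high starter.
- r = 0.3: 0.589 against 0.107.
- r = 0.9: 0.188 against 0.090.

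**Step 4: what a control-period comparison could show.** Write the three scores as Y1, Y2, Y3. Y2 enters Y2-Y1 with a plus sign and Y3-Y2 with a minus sign. The covariance of the two changes is (r-1)·σ² and each variance is 2(1-r)·σ², so their correlation is -0.5. With p the share from Step 2 and p11 the probability of meeting the rule in both periods, the 95% half-width for the paired difference is 1.96·√(2(p - p11)/39):

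- r = 0.3: p11 = 0.050, half-width 0.239
- r = 0.5: p11 = 0.038, half-width 0.233
- r = 0.9: p11 = 0.002, half-width 0.164

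With 39 patients the comparison is therefore uncertain by about 16 to 24 percentage points either way.

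**The case against.** The analysis is labelled post hoc and is mainly four scatter plots; no test or decision hangs on the label. All efficacy hypotheses use the control period, and Table 3 sets the mean changes of both periods side by side, so drift in the mean would be visible. This stands, and it limits the consequence to the responder label and the responder characteristics. It does not supply the missing control-period rate.

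The size of the problem depends on correlations that the SAP does not give, and 14% is not a floor, as r = 0.95 shows. This also stands. The calculations further treat all variation in change as unrelated to exercise, so they are illustrations and not predictions.

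The regression-to-the-mean point is conditional. Table 2 gives HAGOS pain at the start of the control period. If that score is meant, it is uncorrelated with the exercise-period change under the assumptions above, and the contrast in Step 3 disappears. The point also touches only one of the four X-axes directly through a shared score. Both remarks are right, and the first is a reason to state which visit is meant.

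Finally, the control-period rate is an imperfect benchmark: the interval is wide, and an unusual start-of-exercise score pushes the two changes in opposite directions. That is why the comparison should be descriptive. It is still more informative than an exercise-period count with no comparator.

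**Conclusion.** The concern holds. As written, the rule attributes to exercise a gain that a sizeable minority could show with no mean change at all: 31% with the plan's own SD read as an SD of change, and 34% down to 14% for r from 0.3 to 0.9 if it is a single-visit SD, lower still for higher r. These figures rest on zero mean change and approximate normality. If baseline means the start of exercise, a patient starting 1 SD low would meet the rule with probability 51%, against 13% for one starting 1 SD high, at r = 0.5. The primary and secondary results do not change. The change is worth making because responder characteristics are one of the two outputs that the Clinical perspective names.

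**What to change.** - Apply the same 10-point rule to the control-period change in the same patients. Report both proportions and their paired difference with a 95% confidence interval from a paired-proportion method, for example Newcombe's, without a formal test.
- Show control-period changes in matching plots with the same lines at ±10. Plot each period's change against that period's own starting score, so that both plots carry regression to the mean.
- State which visit the baseline score refers to.
- Note that the start-of-exercise score enters the two changes with opposite sign, and that this limits the comparison.
- Replace the responder label with a neutral one: patients improving by at least 10 points during the exercise period.

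The cost is a few lines of analysis and some extra plots; no new data are needed. The exercise-period proportion may look less favourable beside its control-period counterpart, and the interval will be wide.
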